6.5 Reporting of serious adverse events

All SAEs have to be reported, whether or not considered causally related to AZD1775, or to a study procedure(s). All SAEs will be recorded in the eCRF/CRF.

If any SAE occurs in the course of the study, then Investigators or other site personnel will inform appropriate AstraZeneca representatives immediately, or **no later than 24 hours** of when he or she becomes aware of it.

The designated Innovations representative works with the Investigator to ensure that all the necessary information is provided within 1 calendar day of initial receipt for fatal and life threatening events and within 5 calendar days of initial receipt for all other SAEs.

For fatal or life-threatening adverse events where important or relevant information is missing, active follow-up is undertaken immediately. Investigators or other site personnel inform AstraZeneca representatives of any follow-up information on a previously reported SAE within one calendar day i.e., immediately but no later than 24 hours of when he or she becomes aware of it.

SAE information will be sent via secure e-mail connection or via fax. The Innovations Safety Department standard paper SAE Report with supporting relevant source documents (e.g. history and physical [H&P], hospital discharge summary, autopsy report when available, results of relevant diagnostic tests completed to evaluate the event) will be attached and sent via:

- Secure email (Innovations SAE mailbox: [contact]) or by
- Fax (Innovations safety fax number): [name]

Transmission of the SAE report Form should be confirmed by the site personnel submitting the report.

Once the Investigators or other site personnel indicate an AE is serious in the WBDC system, an automated email alert is sent to the designated AstraZeneca representative.

If the WBDC system is not available, then the Investigator or other study site personnel reports a SAE to the appropriate AstraZeneca representative by telephone.

The AstraZeneca representative will advise the Investigator/study site personnel how to proceed.

Investigators or other site personnel send relevant CRF modules by fax to the designated AstraZeneca representative

Follow-up information for SAEs and information on non-serious AEs that become serious should also be reported to Innovations Safety Department as soon as it is available; these reports should be submitted using the Innovations SAE Report Form. The detailed SAE reporting process will be provided to the sites in the SAE reporting guidelines contained in the trial reference manual.

The appointed study Medical Monitor works with the Investigator to ensure that all the necessary information is provided to the Innovations Safety Department **within 1 calendar day** of initial receipt of the information for fatal and life threatening events and **within 5 calendar days** of initial receipt of the information for all other SAEs.

For fatal or life-threatening adverse events where important or relevant information is missing, active follow-up is undertaken immediately. Investigators or other site personnel inform

AstraZeneca representatives of any follow-up information on a previously reported SAE within one calendar day i.e., immediately but **no later than 24 hours** of when he or she becomes aware of it.

Investigators must report SAEs and follow-up information to their responsible Institutional Review Board (IRB) according to the policies of the responsible IRB. For fatal or life-threatening AEs where important or relevant information is missing, active follow-up is undertaken immediately.

AstraZeneca or their representative will provide Regulatory Authorities, Ethics Committees (EC) and PIs with clinical safety updates/reports according to local requirements.

6.6 Overdose

A dose of AZD1775 in excess of that specified according to the protocol will constitute an overdose. There is currently no known antidote to AZD1775, and the treatment of overdose should be supportive for the underlying symptoms. Such overdoses should be recorded as follows:

- An overdose with associated AEs is recorded as the AE diagnosis/symptoms on the relevant AE modules in the eCRF and on the Overdose eCRF module.
- An overdose without associated symptoms is only reported on the Overdose CRF module.

If an overdose of AZD1775 occurs in the course of the study, then the Investigators or other site personnel will inform the Innovations Safety Department immediately or **no later than 24 hours** of when he or she becomes aware of it.

The Innovations Safety Department representative works with the Investigator to ensure that all relevant information is provided.

For overdoses associated with SAE, standard reporting timelines apply (see Section 6.5). For other overdoses, reporting should be done within 24 hours.

6.7 Pregnancy

All pregnancies and outcomes of pregnancy should be reported to the Innovations Safety Department during the course of the study and within 1 month of the last dose of study treatment.

6.7.1 Maternal exposure

If a patient becomes pregnant during the course of the study, AZD1775 should be discontinued immediately and the patient should be removed from the study. Pregnancies

must be avoided in females of child-bearing potential during treatment with AZD1775, and up to a period of ONE (1) menstrual cycle after stopping treatment with AZD1775.

Pregnancy itself is not regarded as an AE unless there is a suspicion that the investigational product under study may have interfered with the effectiveness of a contraceptive medication. Congenital abnormalities/birth defects and spontaneous miscarriages should be reported and handled as SAEs. Elective abortions without complications should not be handled as AEs. The outcome of all pregnancies (spontaneous miscarriage, elective termination, ectopic pregnancy, normal birth or congenital abnormality) should be followed up and documented even if the patient was discontinued from the study.

If any pregnancy occurs in the course of the study, then Investigator or other site personnel informs the Innovations Safety Department immediately, or **no later than 24 hours** of when he or she becomes aware of it.

The designated AstraZeneca representative works with the Investigator to ensure that all relevant information is provided to the AstraZeneca Patient Safety data entry site within 1 or 5 calendar days for SAEs (see Section 6.4) and within 30 days for all other pregnancies.

The same timelines apply when outcome information is available.

6.7.2 Paternal exposure

Men must avoid fathering a child, unprotected sex, and must not donate sperm during treatment with AZD1775 and 3 months following the last dose.

Pregnancy of a patient's partner is not considered to be an adverse event. However, the outcome of all pregnancies (spontaneous miscarriage, elective termination, ectopic pregnancy, normal birth or congenital abnormality) should if possible be followed up and documented.

To capture information about a pregnancy from the partner of a male patient, the male patient's partner consent must be obtained to collect information related to the pregnancy and outcome; the male patient should not be asked to provide this information. The outcome of any conception occurring should be followed up and documented.

6.8 Dose modifications

Toxicity will be assessed utilizing the NCI CTCAE v4.03 (<http://evs.nci.nih.gov/ftp1/CTCAE/CTCAE>), unless otherwise specified.

The DLT criteria in Section 7.2.1 will be used to assess the safety lead-in cohort during Part A Cycle 1. Toxicity occurring in patients beyond Cycle 1 of the Part A safety lead-in will be graded and the appropriate dose modification or supportive care will be administered to decrease the signs and symptoms thereof according to this section.

The DLT criteria evaluations do not apply to Part B. Dose adjustments will be based on the organ system exhibiting the greatest degree of toxicity. Dose reductions or holds and initiation of supportive care are allowed as clinically indicated by the treating physician. A maximum of 2 dose reductions for the AZD1775 will be allowed. Patients requiring >2 dose reductions will be discontinued from the study drug. Dose reductions are presented for AZD1775.

Table 6 AZD1775 Dose Level Reductions for Toxicity

Dose Level	AZD1775 ^a	Schedule 21-day cycle
Starting Dose ^b	175 mg PO BID	Days 1-3 and 8-10
Dose Level -1	150 mg PO BID	Days 1-3 and 8-10
Dose Level -2	125 mg PO BID	Days 1-3 and 8-10

^a AZD1775 taken in 12 hour intervals

^b **Note:** the AZD1775 starting dose is reduced to 175 mg BID because 200 mg BID was not well-tolerated.

Any patient requiring a toxicity-related dose delay of more than 21 days from the intended day of the next scheduled dose must be discontinued from the study unless there is approval from the Medical Monitor for the patient to continue.

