3.10 Criteria for withdrawal

Reasons for withdrawal from the study:

- Withdrawal of consent
- Incorrectly enrolled/treated patient

- AE
- Death
- Patient is lost to follow-up

If a patient wishes to withdraw his/her consent to both treatment and study assessments, they should be asked if they are willing to continue with survival follow-up (which can be conducted by telephone). If a patient wishes to withdraw his/her consent to further participation in the study entirely, including survival follow-up, this should be clearly documented in the patient medical record and in the clinical study database (eCRF).

The status of ongoing, withdrawn (from the study) and “lost to follow-up” patients at the time of analysis should be obtained by the site personnel by checking the patient’s medical record, hospital records, contacting the patient’s general practitioner and checking publicly available death registries. In the event that the patient has actively withdrawn consent to the processing of their personal data, the vital status of the patient can still be obtained by site personnel from publicly available resources, only where it is possible to do so under applicable local laws.

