- c Vital signs (resting heart rate, blood pressure, temperature and weight) at the Screening visit will include height. After Screening, height will not be measured. Vital signs and weight will be obtained prior to study drug administration according to institutional practice, end of treatment (EOT) visit, PFS follow-up assessment, and the final protocol visit (FPV).

- d Clinical chemistry will include measurements of glucose, BUN, creatinine, sodium, potassium, chloride, total calcium, CO₂, alkaline phosphatase (ALP), AST, ALT, total bilirubin, total protein, and albumin.
- e Coagulation performed at baseline only (PT or INR with PTT). Repeat at the beginning of every cycle if patient on Coumadin.
- f An ECG will be collected at baseline to confirm eligibility (see Section 3.2). Cycle 1 Day 1 pre-dosing triplicate 12-lead ECGs will be collected within approximately 2-5 minutes intervals to determine the mean resting corrected QTc using the Fridericia formula (QTcF) <470 msec for females and <450 for males if clinically indicated. Thereafter, patients will have an ECG only as clinically indicated. Repeated ECGs should be performed on the same equipment if possible.
- g Pregnancy tests will only be performed in women of childbearing potential 3 days prior to first dose of study treatment. This will be repeated at the beginning of each treatment cycle. the EOT visit. and at the FPV (see Section 5.2.6).
- h Patients will be restaged after every 2 cycles (every 6 weeks [± 7 days]). Patients with progressive disease or unacceptable toxicity should be discontinued from the study treatment; patients with SD or response to therapy will continue treatment. Tumour status will be compared to baseline and confirmation of response will be evaluated by physical examination, anatomic imaging measurement, and performance status
- i CT scans/MRIs of the chest and abdomen and pelvis are required at baseline and every 2 cycles (6 weeks).
- j The same method of assessment and the same technique must be used to characterize each identified and reported lesion at baseline and during subsequent imaging procedures. Patients continuing study treatment for a minimum of 1 year may have the tumour imaging assessments expanded to every 4 cycles (12 weeks [± 7 days]).
- k Patients without evidence of undue toxicity may continue treatment with study drugs until disease progression occurs as long as they are achieving clinical benefit and desire to continue therapy.

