- l Patients discontinuing AZD1775 should be scheduled for an EOT visit as soon as possible after their last dose. If treatment is discontinued during a study visit, the EOT visit does not need to be repeated. The reason for stopping treatment and date must be recorded in the electronic case report form (eCRF). The EOT visit is **not** required for subjects continuing treatment after the FPV.
- m After discontinuation from AZD1775, patients must be followed for AEs for 30 days, after their last dose or until new therapy. This can be done via telephone contact at the Investigator's discretion. All concomitant medications received 30 days after the last dose of study medication should be recorded in the medical record and eCRF. All new AEs occurring during this period must be reported and followed until resolution, unless, in the opinion of the Investigator, these values are not likely to improve because of the underlying disease. In this case, the Investigator must record his or her reasoning for this decision in the patients' medical records and as a comment in the eCRF. All patients who have Grade 3 or 4 laboratory abnormalities per NCI CTCAE v4.03 at the time of discontinuation must be followed until the laboratory values have returned to Grade 1 or 2, unless it is, in the opinion of the Investigator, not likely that these values are to improve. In this case, the Investigator must record his or her reasoning for making this decision in the patients' medical records and as a comment on the eCRF.
- n A patient discontinuing from AZD1775 in the absence of progressive disease (PD) should continue to have the PFS follow-up assessments until PD has been assessed by the Investigator or the patient begins a new course of cancer therapy or withdraws from the study. Post follow-up for patients with disease progression will be every 12 weeks (± 1 week) from the last date study drug was administered (refer to Sections 4.3 and 4.3.2.1).

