6.8.1 Dose modifications due to hematologic toxicity

Complete blood counts (CBC) will be obtained for all patients at the beginning of each treatment cycle (Day 1). If hematologic toxicity occurs, treatment should be held and ANC and platelets should be monitored weekly (or more often as clinically indicated) until recovery.

Table 7 Day 1 Haematologic Dose Modifications and Management

Treatment Day Blood Counts and Toxicity			
ANC		Platelets	Action
≥1000/μL	And	≥75,000/μL	No dose modification or interruption
<1000/μL	Or	<75,000/μL	Delay by 1 week intervals until recovery

If haematologic parameters do not recover within 21 days, the patient should be removed from the study treatment.

Table 8 Neutropenia, Infection, Febrile Neutropenia Dose Modifications and Management

Any Day	
Grade 3 neutropenic fever (ANC <1000/ μ L + Temperature \geq 101°F [38.5°C]) or neutropenic infection Documented infection with Grade 3 neutropenia (ANC <1000/ μ L) Grade 4 neutropenia (ANC <500/ μ L >7 days) Grade 4 thrombocytopenia (platelet count <25,000/ μ L >7 days)	Hold dose until recovery. Then, upon resuming dosing, reduce AZD1775 to the next lower dose level^a.
Grade 4 febrile neutropenia or Grade 4 infection with neutropenia (both defined as septic shock) Thrombocytopenic haemorrhage (gross occult bleeding) associated with a platelet count <50,000/ μ L	Discontinue treatment and follow for disease progression.

a No more than two dose reductions will be allowed for any patient. Patients requiring additional dose modifications due to toxicity will discontinue study treatment.

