6.8.2 Non-haematologic toxicity dose modifications

Substantial acute toxicities should be managed as medically indicated and with temporary suspension of investigational product, as appropriate. Dose reductions or holds and initiation of supportive care are allowed as clinically indicated by the treating physician.

Dose reductions of AZD1775 should be considered if the toxicity is considered to be related to AZD1775 (i.e., in monotherapy studies or in combination studies) if the relationship cannot be wholly attributed to the combination agent (each combination agent should be considered on an individual basis). Dose re-escalation is not permitted.

In general, if a patient experiences a Grade 1/Grade 2 non-haematological toxicity, no dose modification is required (except QTc prolongation; see table below). If a patient experiences a Grade 3 or Grade 4 toxicity which is not attributable to the disease or disease-related processes under investigation, dosing will be interrupted and/or the dose reduced, and supportive therapy administered as required. Any patient who develops a Grade 3 or 4 non-haematologic toxicity that does not resolve to \leq Grade 1 within 21 days should be removed from the study treatment unless approved by the Medical Monitor.

Table 9 AZD1775 dose modifications for QTc interval prolongation

Electrocardiogram QT corrected interval prolonged	
QTc Value	AZD1775
QTc 450-480 ms (males) or 470-480 (females)	Hold. Once QTc interval has returned to pretreatment status and correction of possible electrolyte imbalance has been made, resume at next lower dose level.
QTc 481-500 ms	Hold. Seek cardiologist advice.
QTc \geq 501 ms	Discontinue treatment
Shift from baseline of \geq 60ms	Discontinue treatment

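### Section 6.8 takes a patient with a toxicity delay over 21 days off the study, while the overlapping rules in 6.8.1 and 6.8.2 stop treatment only; followed literally, it ends tumour scans

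*Protocol*

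**What the plan says.** Section 6.8 closes with a rule for any patient whose toxicity-related delay exceeds 21 days, counted from the date set for the "next scheduled dose must be discontinued from the study unless there is approval from the Medical Monitor for the patient to continue". Earlier in the same section, the limit on dose reductions is worded differently: "Patients requiring >2 dose reductions will be discontinued from the study drug".

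The neighbouring rules stop treatment:

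- Section 6.8.1, haematologic toxicity: "If haematologic parameters do not recover within 21 days, the patient should be removed from the study treatment".
- Section 6.8.2: a patient whose Grade 3 or 4 non-haematologic toxicity has not settled to Grade 1 or better "within 21 days should be removed from the study treatment unless approved by the Medical Monitor".
- Table 8, for neutropenic septic shock or thrombocytopenic haemorrhage: treatment stops and the patient is still followed for progression.
- Table 2 note h, more generally: "Patients with progressive disease or unacceptable toxicity should be discontinued from the study treatment".

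On follow-up, Table 2 note n states: "A patient discontinuing from AZD1775 in the absence of progressive disease (PD) should continue to have the PFS follow-up assessments". Section 4.3.2.1 says the same but ends these assessments at progression, new cancer therapy or withdrawal from the study. Section 5.1.1 likewise ends tumour assessments at progression or study withdrawal. In Section 3.10, the list headed "Reasons for withdrawal from the study" includes AE.

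**The concern.** A site faced with one event, a dose held for more than 21 days because of toxicity, finds two dispositions. Under 6.8 the patient leaves the study. Under 6.8.1 or 6.8.2 the patient leaves treatment and stays in follow-up. The difference matters because the scan schedule continues after drug discontinuation but not after study withdrawal.

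ORR, DCR, DoR and PFS are the Part B primary outcome measures (Section 2.1). Section 8.6.1.2 counts PFS events whether or not the patient has withdrawn from therapy, which presupposes scanning after the drug stops. Section 8.6.1.1 counts only confirmed responses in ORR, over all treated patients. Scans stopped because of toxicity would make the censoring of PFS and DoR depend on toxicity, and so potentially informative. An analysis plan cannot recover scans that were never taken.

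**Working it through.** The protocol states no figure here to reproduce. The check sets the rules side by side, follows the consequence, and tests by dates whether a response confirmation can be lost.

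**1. The rules compared**

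| Place | Trigger | Patient leaves | Medical Monitor exception |
|---|---|---|---|
| 6.8, closing rule | Toxicity-related dose delay over 21 days | Study | Yes |
| 6.8, reductions | More than 2 dose reductions | Drug | None stated |
| 6.8.1 | Counts not recovered in 21 days | Treatment | None stated |
| Table 8 | Neutropenic septic shock; thrombocytopenic haemorrhage | Treatment, with follow-up for progression | None stated |
| 6.8.2 | Grade 3/4 non-haematologic toxicity unresolved in 21 days | Treatment | Yes |
| Table 2 note h | Unacceptable toxicity, no 21-day clock | Treatment | None stated |

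The direct conflict is with 6.8.1 and 6.8.2. A patient whose low neutrophil count keeps dosing on hold beyond 21 days meets both 6.8 and 6.8.1. The 6.8.2 trigger overlaps but is not identical, because its clock runs on resolution of the toxicity and not on the dose. Note h is general support only. Taken literally, the set of rules ends follow-up after a long delay but continues it after septic shock, which is hard to see as intended.

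**2. The consequence for PFS and DoR**

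A progression-free patient withdrawn from the study has no further scheduled scans (4.3.2.1, 5.1.1). Section 8.6.1.2 then censors PFS at the last evaluable RECIST assessment, and Section 8.6.1.4 gives DoR the same censoring time. One qualification applies. Section 3.10 seeks vital status for withdrawn patients, so a death soon enough after the last scan could still count as an event.

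**3. Can a confirmation be lost?**

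Inputs: 21-day cycles; restaging every 6 weeks ± 7 days; confirmation no less than 4 weeks (28 days) after the response is first seen (Appendix D); a CT/MRI marked at the end-of-treatment visit in Table 2. Assume that the end-of-treatment scan falls on the day the 21-day limit is passed.

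- Week 6 scan: Day 1 + 42 = Day 43, window Day 36 to 50. Cycle 3 Day 1: 1 + 2 × 21 = Day 43. Cycle 3 Day 8: 43 + 7 = Day 50.
- *Case A.* Response on Day 43, Day 43 dose held. The limit is passed on 43 + 22 = Day 65. Confirmation needs 43 + 28 = Day 71 or later. The end-of-treatment scan comes 65 − 43 = 22 days after the first, which is too early. The next 6-week scan, 1 + 84 = Day 85 (78 to 92), would not be taken under a literal 6.8. Confirmation is lost.
- *Case B.* Response on Day 36, Day 43 dose held. Confirmation is possible from 36 + 28 = Day 64, so a scan on Day 65 can confirm. Nothing is lost.
- *Case C.* Response on Day 43, hold starting with the Day 50 dose. The limit is passed on 50 + 22 = Day 72, and 72 − 43 = 29 days, which is at least 28. Nothing is lost.

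So the loss is possible, but it depends on when the scan and the hold fall.

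**The case against.** The strongest reply is that 6.8 is loosely worded and nobody would follow it to the letter. The sentence sits in a dose-modification section, and its exception, approval to continue after a dose delay, most naturally means continuing to dose. Section 3.9 lists an adverse event as a reason to stop AZD1775. Table 8, Section 6.4.1, Section 4.3.2.1 and note n all expect follow-up to go on after a stop for toxicity. The Medical Monitor exception also gives the site a central contact who could clear up the wording. All of this stands as evidence of intent, and it makes literal application less likely. It does not remove the conflict: the operative words still say study, and Section 3.10 offers a matching withdrawal reason.

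A reader might infer that the protocol keeps treatment discontinuation and study withdrawal strictly apart, so that 6.8 must mean what it says. The documents do not support that. Section 3.9.1, on stopping the product, asks sites to report the withdrawal, and Section 4.2 cites 3.9 and 3.9.1 for both discontinuation and withdrawal criteria. Section 6.7.1 says of a pregnant patient that "AZD1775 should be discontinued immediately and the patient should be removed from the study", yet pregnancy is on the 3.9 list and not on the 3.10 list. The usage is loose throughout.

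A reader might also want to argue from a 12-week scan interval off treatment. Part B note n attaches that interval to patients with progression, while Part A note n attaches it to patients without, so nothing should be built on it.

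**Conclusion.** The conflict is real and minor. Section 6.8 gives a disposition that differs from 6.8.1 and 6.8.2 for overlapping events, and applied literally it ends the scans that the Part B primary measures use. The intent was probably to stop treatment.

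The size cannot be computed. The protocol gives no rate of toxicity delays over 21 days. Only patients who are progression-free, have no Medical Monitor approval to continue, and are treated at a site that reads 6.8 literally would be affected. That number is probably small. A reader might turn one lost confirmation into a percentage-point change in a cohort's ORR, but that would only restate the cohort size. Cases B and C show that a confirmation need not be lost at all, and nothing in the protocol says how often Case A would arise. No ORR or PFS shift is claimed. The study is descriptive, with no formal hypothesis test (Section 8.3), so no test result is at stake.

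**What to change.** Reword the end of the Section 6.8 rule along these lines: *must be discontinued from study treatment unless the Medical Monitor approves continuation; patients without progression continue tumour assessments per Section 4.3.2.1.*

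The cost is one sentence. It adds no type of visit or data that the follow-up sections do not already require, and it changes no safety threshold. The 21-day clock in 6.8.2 stays as it is. Whether 6.8.1 should also carry a Medical Monitor exception is a safety decision for the sponsor and is separate from this point.
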